Hence, we will also look for any differences in pain, nausea and vomiting over the first 24 hrs after the surgery, along with chances of readmission or ER visits within the same period, post discharge. At 3 months, we will look for the incidence of persisting pain after surgery.

Hypothesis

In patients who undergo ambulatory surgical procedures causing at least moderate pain, hydromorphone (HM) increases the proportion of patients who would demonstrate 'satisfactory analgesia [$=<4/10$ NAS] with minimal or no postoperative nausea-vomiting (PONV) [$<2/5$ VDS] as compared to morphine (M), when both are administered intravenously, in equianalgesic doses, and are compared at 2 hours after surgery in PACU.

2. Specific Objectives

The primary objective of this study is to compare the proportion of patients with SAME (satisfactory analgesia and minimal emesis) after AS, when using M compared with HM, during the immediate postoperative hospital stay.

Secondary objectives include:

1. Total dose of analgesic used in PACU, in morphine equivalents,
2. Time to discharge or readiness to discharge from the DSU,
3. Proportion of pain, and its comparison after discharge, within 24 hours,
4. Proportion of nausea, and its comparison after discharge, within 24 hours,
5. Proportion of vomiting, and its comparison after discharge, within 24 hours,
6. Incidence of CPSP at 3 months after discharge

The tertiary objectives include:

1. Proportion of patients with severe itching,

Protocol Version Date: Version 5 / June 23, 2015

Most Effective Opioid Analgesia in Ambulatory Surgeries: a randomized control, investigator blinded, parallel group with superiority design study of Morphine versus Hydromorphone

[name], Principal Investigator SJHH

[name], Principal Investigator HHS

2. Proportion of patients with significant sedation,
3. Proportion of patients with significant respiratory depression,
4. Patient satisfaction score at the time of discharge,
5. Time to discharge or readiness to discharge from the PACU,
6. Use of ketorolac as a rescue medication,

METHODS

The study is designed as a multisite, 2 arm, parallel, superiority design with randomization of patients and blinding of patients, health care providers (physicians and nurses) and research personnel (research coordinator and data analyst). Patients will be stratified based on site and laparoscopic/open surgeries. Intention to treat approach will be used for design and analysis.

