PACU Stay: The actual study intervention (hence randomization) will only become applicable once the patient is moved to the PACU. Every patient will be treated as per the protocol during the intraoperative management, which primarily restricts the use of any study opioids. The details are provided in appendix 2. The nurse looking after the study patient in PACU will administer the medication as per the study protocol. This would include analgesia with equipotent doses of M or HM administered in titrated doses. Syringes will be pre-prepared from the pharmacy in EMUs; 1ml=1mg of morphine or 0.2 mg of hydromorphone. We shall consider a potency ratio of 1:5 (M: HM), considered equivalent in literature.⁽⁹⁾ Analgesia will be provided according to the following guideline. A similar method has been advised to be safe and effective for titrated analgesia in PACU.⁽²⁴⁾ Readiness to discharge from PACU and outcomes are noted at 2 hrs, or at the time of discharge to DSU.

Most Effective Opioid Analgesia in Ambulatory Surgeries: a randomized control, investigator blinded, parallel group with superiority design study of Morphine versus Hydromorphone
[name], Principal Investigator SJHH
[name], Principal Investigator HHS

PACU Protocol (titrate the opioid medication to achieve desired pain score)

- Patient to be asked for their pain score, and if it is more than 4 out of 10 (NAS): to receive the 1st dose within 5 minutes after coming to PACU: 0.04mg/kg morphine units (rounding off to the nearest 1 ml or 0.5 ml); with a maximum of 3 mg of morphine equivalents.
- Repeat doses: 0.02 mg/kg morphine units every 5-10 minutes to titrate for analgesia and side effects (rounding off to the nearest 1 ml or 0.5 ml)
- If no side effects observed-titrate to have analgesia: NAS =<4/10.
- If Nausea-Vomiting observed: record it in the CRF provided and treat it with antiemetics (Ondansetron 1-4 mg IV, Dimenhydrinate 25-50 mg)
- If patient is too sedated (<3-Ramsey Sedation Scale)-withhold the next dose and restart the bolus if the score is >3
- If respiratory depression present, withhold the next dose, treat with Naloxone if necessary.
- Ketorolac IV 15-30 mg as rescue medication if patient does not tolerate the study opioid or if the patient does not satisfy the success of satisfactory analgesia at more than 1 hr.

DSU Stay and Protocol:

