OUTCOME MEASURE	TYPE	MEASUREMENT	TIME OF MEASUREMENT	ANALYSIS METHOD
Primary outcome Satisfactory Analgesia with minimal PONV	Binary	NAS=<4/10 VDS<2/5	At 2hrs or at the time of discharge from PACU	Chi-square
Severe Itching	Binary	VAS>5/10	At 2hrs or at the time of discharge from PACU	Chi-square or Fisher's test (as appropriate)
Severe Sedation	Binary	Ramsey Score >3/6	At 2hrs or at the time of discharge from PACU	Chi-Square or Fisher's test (as appropriate)
Severe Respiratory Depression	Count	All cases needing treatment as counts	At 2hrs or at the time of discharge from PACU	Chi-square or Fisher's test (as appropriate)
Use of Ketorolac	Continuous	Total dose used per patients as a rescue therapy	At 2hrs or at the time of discharge from PACU	T test
Mean dose of Analgesic Used	Continuous	Dose of Analgesic used per patient in EMU	At the time of hospital discharge	T test

Most Effective Opioid Analgesia in Ambulatory Surgeries: a randomized control, investigator blinded, parallel group with superiority design study of Morphine versus Hydromorphone
 [name], Principal Investigator SJHH
 [name], Principal Investigator HHS

Patient Satisfaction-Mean score (0-10)	Continuous	Mean Score calculated between 0 to 5 scale	At the time of hospital discharge	T test
Time to discharge from PACU	Continuous	Mean time in hrs	At 2hrs or at the time of discharge from PACU	T test
Time to discharge from the hospital	Continuous	Mean time in hrs	At the time of hospital discharge	T test

Outcomes at Post-operative Day 1:

Patients will be approached by 1-2 phone calls shall be done during the next day; if unanswered, a repeat call will be made on the subsequent day (2nd day after discharge); for responders, the following questions will be asked.

1. What was your average pain score over the last 24 hrs, in 0-10 NAS scale, after you were discharged home?
2. After discharge, did you have nausea-severe enough to require medications at home?
3. After discharge, did you have vomiting-severe enough to require medications at home?
4. After discharged home, did you require a visit to ER, or readmission?

Outcomes at 3 months:

Patients will be contacted by a mailed package at 3 months after surgery to collect the following outcomes.

1	Do you have Persistent Pain (which started with or after surgery), at or near the surgical area?	Yes or No
2	Intensity of Pain	NAS: 0-10
3	Brief Pain Inventory-Interference Items 7 Items: each item scored between 0-10	

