4	Global Impression of Change	Likert scale 1-7

Most Effective Opioid Analgesia in Ambulatory Surgeries: a randomized control, investigator blinded, parallel group with superiority design study of Morphine versus Hydromorphone
[name], Principal Investigator SJHH
[name], Principal Investigator HHS

5	Analgesic Use: Did you have to use any pain medications for more than 1 month, to help with pain, which started with or after Surgery?	Yes or No
---	---	-----------

Statistical Analysis: The study will be analyzed using an intention to treat approach. The individual outcomes along with their respective analyses method have been listed within the table 1. Broadly the dichotomous outcomes will be reported as proportions and analyzed using a chi-square test to detect a significant difference ($p<0.05$). Precision will be reported using 95% CI. Continuous outcomes will be analyzed using an unpaired 2-tailed student t test for significance ($p<0.05$). Means and standard deviations shall be reported along with 95% CI. We also plan to perform logistic multivariable regression analysis to account for the influence of baseline covariates, which are listed in appendix 1. A sensitivity analysis will be performed to compare the effects of laparoscopic surgeries vs open surgeries.

Trial Management: This trial will be conducted at 3 hospital sites affiliated with McMaster University, Hamilton: St Joseph's Hospital, McMaster University Hospital and Juravinski Hospital.

Data Management and Quality Control: All study data including CRFs of each patient, shall be securely stored at the central office. A summary table indicating study timeline from enrollment to final follow-up (<http://www.spirit-statement.org/title/>) shall be included for each patient.⁽²⁷⁾ CRF's will be collected as paper forms. They shall be periodically cross-checked for completeness and entered into a suitable electronic master file. All reports of incorrect randomizations, protocol violations or incomplete data shall be noted.

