APPENDIX 1: Study Patient Case Record Form with Details to be Recorded

DEMOGRAPHICS AND PATIENT INFORMATION TO BE OBTAINED FROM PATIENT RECORDS

Study Number: Site: SJH MUMC JH

1	Patient's Hospital ID Number		
2	Age		
3	Gender	M	F
4	Height		
5	Weight		
6	Allergy to NSAIDS	Y	N
7	Allergy to LAs	Y	N

INFORMATION TO BE GAINED FROM THE PATIENT MEETING

1	APFEL Score (for PONV prediction)		Collected on 4 items- separately
2	HADS Score (Hospital Anxiety Depression Scale)		Collected on 14 items- separately
3	PCS (Pain Catastrophizing Scale)		Collected on 13 items - separately
4	Presence of Preoperative Pain in the Surgical Area	Y	N
5	If YES: is it Mild/ Moderate/ Severe		
6	Presence of Chronic Pain (>4 months) in Other Parts of the Body	Y	N

Most Effective Opioid Analgesia in Ambulatory Surgeries: a randomized control, investigator blinded, parallel group with superiority design study of Morphine versus Hydromorphone
 [name], Principal Investigator SJHH
 [name], Principal Investigator HHS

7	If YES: is it Mild/ Moderate/ Severe		
---	--------------------------------------	--	--

SURGICAL DETAILS TO BE OBTAINED FROM THE SURGICAL RECORDS

1	Date of Surgery		
2	Diagnosis (Intraoperative)		
3	Actual Surgical Procedure		
4	Laparoscopic or Open	L O	
5	Surgeon		Initials
6	Start Time of Surgery		
7	End Time of Surgery		
8	Duration of Surgery		
9	Total Local Anesthetic Infiltration (mls)		

ANESTHESIA DETAILS TO BE OBTAINED FROM THE ANESTHETIC RECORD

1	Anesthesiologist		Initials
2	Dexamethasone 4mg or 8mg	Y N	
3	Midazolam	1 mg 2 mg	
4	Propofol (total dose used)		
5	Remifentanyl (total dose used)		
6	Fentanyl (total dose used)		
7	Sufentanil (total dose used)		

Most Effective Opioid Analgesia in Ambulatory Surgeries: a randomized control, investigator blinded, parallel group with superiority design study of Morphine versus Hydromorphone
 [name], Principal Investigator SJHH
 [name], Principal Investigator HHS

8	Any continuous infusion used	Propofol  Remifentanyl 	
9	Ondansetron Prophylaxis Dose		Given prior to extubation
10	Was there a delay in transferring patient to the PACU (applicable when the PACU is on hold-and protocol needs to be initiated by the OR anesthesiologist)	Y N	

APFEL SCORE: for Prediction of Post-Operative Nausea Vomiting

RISK FACTOR	SCORE (each gets 0 or 1)
Postoperative Opioids	
Non-smoker	
Female Gender	
History of PONV or Motion Sickness	
Total Score	

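### Post-discharge nausea and vomiting get a valid but unadjusted chi-square test, although PONV risk items already on the case record form could sharpen it modestly

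*Combined protocol and SAP*

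**What the plan says.** - **Objectives.** Specific Objectives lists as secondary objectives 4 and 5: "Proportion of nausea, and its comparison after discharge, within 24 hours" and "Proportion of vomiting, and its comparison after discharge, within 24 hours".
- **Measurement.** Both are yes/no telephone questions put to responders (Outcomes at Post-operative Day 1). The nausea question reads: "After discharge, did you have nausea-severe enough to require medications at home". The vomiting question has the same form.
- **Test.** Neither outcome has a row in Table 1. The rule that reaches them is in Statistical Analysis: "Broadly the dichotomous outcomes will be reported as proportions and analyzed using a chi-square test to detect a significant difference".
- **Adjusted analysis.** The same paragraph plans a multivariable logistic regression on the baseline covariates of Appendix 1. It does not name the outcome, the covariates to be chosen, the form in which APFEL enters, or whether the model is primary or supportive.
- **Risk items.** Appendix 1 lists the "APFEL Score (for PONV prediction") under the patient meeting, marked "Collected on 4 items- separately". The items are "Postoperative Opioids", non-smoker, female, and previous PONV or motion sickness.
- **Stratification.** METHODS names site and laparoscopic/open. Allocation and Randomization names centre only.

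**The concern.** The trial collects a predictor for this kind of outcome, yet the only test assigned to two of its six secondary objectives does not use it. Adjusting for a prognostic baseline variable, and for factors used in stratifying, usually sharpens a randomised comparison at little cost. Here the items are already on the form.

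The planned regression does not settle the matter. With its outcomes and covariates unnamed, those choices would be made after the data are in, and nothing says that it replaces the chi-square.

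A smaller question concerns one APFEL item. Postoperative opioid use can be read as expected use or as actual use, and the form does not say which. Patients are randomised on entry to the PACU. Actual use is decided after that: the dosing instruction begins "Patient to be asked for their pain score, and if it is more than 4 out of 10", and oral opioid in the DSU is given as needed for pain.

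**Working it through.** **The plan's own figure.** The only sample size is for the primary outcome, at 80% vs 90%, two-sided alpha 0.05 and 90% power:

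n = [1.960·√(2·0.85·0.15) + 1.2816·√(0.80·0.20 + 0.90·0.10)]² / 0.10² = (0.9897 + 0.6408)² / 0.01 = 265.9, so 266 per group.

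This matches. No figure is stated for objectives 4 and 5, and nothing below changes the 266.

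**Assumptions.**
- Event rates: the background section gives up to one third or more for any nausea or vomiting after surgery. Rates of 15%, 10% and 5% are also tried, because needing medication at home is a stricter definition.
- Odds ratio (OR) per APFEL point: 1.5, 2.0 or 2.5.
- Three-item score, either (A) 0/1/2/3 in shares 10/30/40/20%, or (B) item prevalences 0.75, 0.65 and 0.40.
- Patients: 275 per arm, or 275 × 0.8 = 220 with 20% telephone non-response.

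**Chi-square power by formula.** For 33% vs 22% at 275 per arm:

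Φ{[0.11·√275 − 1.960·√(2·0.275·0.725)] / √(0.33·0.67 + 0.22·0.78)} = Φ{(1.824 − 1.238) / 0.627} = Φ(0.94), about 82-83%.

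The simulated chi-square power below agrees with this.

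**Adjusting for the score alone (simulation, 2,500-4,000 trials per setting, Wald test).** The variance ratio is the variance of the raw risk difference divided by that of the standardised one.

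| Rates, score, n per arm | OR per point | Chi-square power | Adjusted power | Variance ratio |
|---|---|---|---|---|
| 33% vs 22%, A, 275 | 1.5 | 82.2% | 83.1% | 1.02 |
| same | 2.0 | 83.8% | 85.5% | 1.07 |
| same | 2.5 | 83.5% | 86.3% | 1.09 |
| same, separate run | 2.0 | 82.0% | 85.2% | 1.08 |
| same, separate run | 2.5 | 83.0% | 86.5% | 1.13 |
| 33% vs 22%, A, 220 | 2.0 | 75.0% | 77.6% | – |
| 33% vs 23%, B, 275 | 1.5 | 74.2% | 74.2% | – |
| same | 2.0 | 75.7% | 77.5% | – |
| same | 2.5 | 76.3% | 80.0% | – |
| 15% vs 8%, A, 275 | 2.0 | 74.2% | 75.4% | 1.03 |

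A ratio of 1.08 is worth 275 × 0.08 = 22 more patients per arm. Type I error at 33% vs 33% (B; OR 1.5, 2.0, 2.5) was 4.8%, 5.0% and 5.9% for chi-square, and 4.9%, 5.1% and 5.5% adjusted.

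**Adding site and laparoscopic/open to the model.**
- 33% vs 22%, 275 per arm: gain of about 0.5-3 points of power and 2-12% precision.
- 15% vs 8%: about 1-2 points at 275 per arm in one run. In another, covering 220 and 275 per arm, −0.5 to +2.5.
- 10% vs 5%: about −1 to +1 points.
- 5% vs 2%: the Wald test loses about 3-6 points, for example 38.6% to 32.3% at OR 2.0 with 220 per arm. In a separate run at 220 per arm it fell from 41% to 34%, while a likelihood-ratio test held 41%. About 1-3% of fits failed. Expected events are 220 × 0.05 + 220 × 0.02 = 15.4, against five coefficients besides the intercept (treatment 1, three sites 2, approach 1, score 1).

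**The opioid item.** If it is scored 1 for everyone, it only shifts the intercept. In a test data set the treatment log OR (−0.0551) and z (−0.298) were the same with and without it.

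**The case against.** **Chi-square is valid under 1:1 randomisation.** This stands. Chance imbalance in PONV risk is already reflected in its confidence interval. A reader might infer bias in the unadjusted result, but the documents give no ground for that. The cost is precision only.

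**Adjustment is already planned.** This stands in part. A reader might infer that the plan has no adjusted analysis, or that its regression takes in every line of Appendix 1. Neither is right: a regression is planned, and it is limited to baseline covariates. It is still not attached to objectives 4 and 5, and the chi-square remains their test.

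**The one-third rate belongs to a broader outcome.** This stands. That rate covers any nausea or vomiting after surgery. The telephone questions count only symptoms needing medication at home, so the rate may well be lower, above all for vomiting.

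**A Wald test can do worse than chi-square when events are rare.** This also stands, and it is why the fix names a likelihood-ratio test and a fallback. The type I error figures above are for the Wald test at 33%. There are none for the likelihood-ratio test at very low rates, which is a further reason for the fallback.

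**The opioid item does no harm.** Largely right. A reader might infer that it is the study treatment itself and would bias any model containing the APFEL total. The documents do not support this. APFEL is taken at the preoperative meeting, so expected use is the natural reading, and that is near-constant. Even on the actual-use reading, the first PACU dose follows pain before any study drug has acted, under blinding, and the trial compares two opioids, not opioid with none.

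**Conclusion.** The point holds as a minor improvement to the analysis of two secondary objectives. The stated test is valid but leaves out risk items already collected and the stratification factors, and the planned regression does not fill that place.

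Under the assumed score distributions and odds ratios of 1.5-2.5 per point, adjustment is worth about 0-4 points of power and 2-13% precision at a rate near one third, about 0-2 points at 15%, and about none at 10% or below. The documents give neither the APFEL gradient nor the rate of nausea or vomiting needing medication at home, so the place within that range is unknown. The primary outcome and its sample size are unaffected.

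The opioid item is uninformative as expected use and settled after randomisation as actual use. Either is reason enough to leave it out of a baseline covariate, but no bias from it has been shown.

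**What to change.** In Statistical Analysis, for secondary objectives 4 and 5:

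- Make the stated test a logistic model with treatment, site, laparoscopic/open and the sum (0-3) of the three pre-treatment APFEL items: non-smoker, female, and previous PONV or motion sickness.
- Test treatment by likelihood ratio, not Wald.
- Report the standardised risk difference with 95% CI, and the unadjusted proportions alongside.
- Return to chi-square or Fisher's test if events are too few for the model to fit, and define that condition in advance.
- Leave the postoperative-opioid item out of the covariate.

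The cost is a few sentences and no new data, since the items are held separately. The downside is a slightly less simple test, with little gain if events are rare or APFEL predicts weakly.

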Allocation and Randomization: Treatment allocation will be done using a random, computer generated table, with an allocation ratio of 1:1, using random permuted block sizes. Stratification based on each centre (3 sites). These syringes (4*10 mls)-in sealed packages, labelled with serial numbers and no identifiers for the medication, shall be deposited in a safe drug locker, within the fridge, at the respective PACU. The actual randomization, for each patient happens as they enter into the PACU after surgery. The PACU nurse allotted for that patient will obtain the next medication package in series to be used for that patient. To ensure that the respective patient and medication is matched for subsequent analysis, the nurse will attach the medication sequence number on the patient study records, with no identifiers of actual drug. The PACU nurse shall also note down the patient hospital ID on the medication syringe, once it is taken out, to ensure there is no mix up.

Blinding: The study allocation will be blinded to patients, treating nurses, physicians, research assistant and investigators. The allocation order will be available only to the person responsible for randomizing and the pharmacists involved in the study at each centre.

Application of Intervention:

The Operating Room Protocol: Patients included in the study need to be managed according the OR protocol provided in Appendix 2. In brief, the patient will only have a GA, with local infiltration provided at the end of the surgery. Long acting opioid medications (morphine and hydromorphone) are not administered in the OR. LA infiltration is done within a range of 20-30 mls (based on laparoscopic or open surgeries) using 0.25% bupivacaine with or without adrenaline.

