At the end of 2 hours or after satisfactory completion of primary endpoints, patients shall be transferred to DSU. At the DSU, in both groups, patients shall be given oral Oxycocet (combination of oxycodone and paracetamol) or Tylenol 3 (combination of codeine and paracetamol), as a PRN medication, if necessitated by the patient's pain. Nurses shall note down the occurrence of any pain and nausea necessitating treatment in the patient's CRF. Readiness to discharge home is noted down for each patient. The RA shall collect the CRFs from PACU and DSU and deposit safely in a locked filing cabinet.

Planned Outcomes: Our combined primary outcome will be proportion of patients with SAME, as compared between the 2 groups. Analgesia will be based on NAS 0-10 (appendix 3), and PONV will be based on VDS 0-5 (appendix 3). These observations will be made at the end of 2 hrs or before (corresponding to the time of discharge from PACU), by the PACU nurse, in the specified CRF. All the other outcomes to be recorded within the hospital, along with the time of their measurement and proposed analysis method are noted in table 1.

Sample Size Calculation: It was calculated based on the primary, binary outcome of proportion of patients with SAME, which will be compared using a chi-square test. According to literature,

Most Effective Opioid Analgesia in Ambulatory Surgeries: a randomized control, investigator blinded, parallel group with superiority design study of Morphine versus Hydromorphone
 [name], Principal Investigator SJHH
 [name], Principal Investigator HHS

approximately 30%-40% of patients are provided with inadequate analgesia after their AS,^(25, 26) with a similar number also known to suffer from PONV after AS.^(3, 24) Our chart reviews suggests that approximately 20% of patients suffer from inadequate analgesia with PONV using morphine. For a 2-sided test, with an alpha of 0.05 and a power of 90%, and with an estimated effect size of 10% (p1= 80% and p2= 90%), a sample size of 266 per group was calculated. However, for recruitment we shall have a target of 275 per group, for a total of 550 patients (rounding off). For the primary outcome analysis, we expect minimal loss through attrition as the study involves a follow up of few hours. The expected recruitment is approximately 20 cases per month at each of the 3 sites. We expect the trial to run for 10-12 months.

Table 1: Study Outcomes, and their Measurement and Analysis

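### Time to discharge is tested without covariates, although site, approach, duration and end time of surgery are fixed before randomisation: a free improvement in precision may be going unused

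*Combined protocol and SAP*

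**What the plan says.** Secondary objective 2 (Specific Objectives) is "Time to discharge or readiness to discharge from the DSU". Table 1 carries a row "Time to discharge from the hospital", classed as continuous, summarised as mean hours and assigned a t test. The Statistical Analysis section gives the general rule: "Continuous outcomes will be analyzed using an unpaired 2-tailed student t test for significance". No covariates are attached to it.

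The same section names one adjusted analysis: "We also plan to perform logistic multivariable regression analysis to account for the influence of baseline covariates", with Appendix 1 cited for the list. It also mentions a sensitivity analysis of laparoscopic against open surgery, without naming a model or an outcome.

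Appendix 1 records site in its header. Its surgical details cover approach (item 4), start and end times (items 6 and 7) and "Duration of Surgery" (item 8). On timing, Allocation and Randomization says: "The actual randomization, for each patient happens as they enter into the PACU after surgery".

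On stratification, the opening of Methods names both site and laparoscopic/open surgery, while Allocation and Randomization names centre only.

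**The concern.** The trial pools several general-surgical and gynaecological procedures, laparoscopic and open, at three sites. Approach, length of operation and how late the list finished could plausibly affect when a day-surgery patient goes home. Under an unadjusted t test, whatever variation they explain stays in the error term. Site, and approach if it is used, are stratification factors. A t test that ignores prognostic stratification factors tends to report a standard error that is too large.

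The plan accepts adjustment for Appendix 1 covariates in principle but supplies a model only for binary outcomes. Study Significance lists earlier discharge and lower cost among the hoped-for advantages. A wider interval than the collected data allow would weaken what the trial can say about them.

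**Working it through.** **1. The plan's own figure.** The sample size rests on the binary primary outcome: 80% against 90%, two-sided alpha 0.05, power 90%. With pooled variance and no continuity correction,

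n = [1.960·√(2·0.85·0.15) + 1.2816·√(0.80·0.20 + 0.90·0.10)]² / 0.10² = (0.990 + 0.641)² / 0.01 ≈ 266 per group.

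This matches "a sample size of 266 per group was calculated". Power is 90.0% at 266 and 90.9% at the recruitment target of 275. Nothing below alters it.

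**2. Are the covariates legitimate?** Surgery ends, the patient enters the PACU, and allocation follows. Site, approach, duration and end time are settled by then and treatment cannot affect them. Anaesthesia item 10 in Appendix 1 allows the OR anaesthesiologist to start the protocol when the PACU is on hold. That item concerns delayed transfer, so surgery should already be over.

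**3. Does any planned analysis already adjust hours?** The t test has no covariates, a logistic model does not estimate a mean difference in hours, and the laparoscopic/open sensitivity analysis is not described as an adjusted model for this outcome. No linear or time-to-event model appears.

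**4. What adjustment could gain.** Assume 275 patients per arm with data, and let R² be the share of outcome variance that the covariates explain. The documents give no value for R², so a range is shown.

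- SE = SD·√(2/275)·√(1 − R²)
- Difference detectable with 90% power = (1.960 + 1.2816)·SE, which is 0.276 SD unadjusted
- Equivalent unadjusted size = 275/(1 − R²) per arm

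| R² | SE multiplier | Detectable difference, 90% power | Power at 0.276 SD | Equivalent n per arm |
|---|---|---|---|---|
| 0 | 1.000 | 0.276 SD | 90.0% | 275 |
| 0.05 | 0.975 | 0.269 SD | 91.4% | 289 |
| 0.10 | 0.949 | 0.262 SD | 92.7% | 306 |
| 0.20 | 0.894 | 0.247 SD | 95.2% | 344 |
| 0.30 | 0.837 | 0.231 SD | 97.2% | 393 |

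**5. What it could cost.** Two site terms plus approach, duration and end time make five covariate terms. If they explain nothing, the standard error rises by a factor of about √(1 + 5/542) = 1.005.

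**6. Simulation check.** There were 3,000 simulated trials per R² value, with approach, duration and end time as covariates and a true difference of 0.276 SD. Power of the t test against the adjusted model was 0.902 and 0.901 at R² = 0, 0.896 and 0.929 at 0.10, 0.893 and 0.944 at 0.20, and 0.890 and 0.970 at 0.30.

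**7. Illustration in minutes.** Both the SD and the 20-minute difference are assumptions. With SD 1.5 h (90 min), the unadjusted SE is 90·√(2/275) = 7.67 min. The difference detectable with 90% power is 24.9 min, falling to 23.6, 22.3 or 20.8 min at R² 0.10, 0.20 or 0.30. Power for 20 min is Φ(20/7.67 − 1.96) = 74% unadjusted. It becomes 76%, 78%, 83% or 88% at R² 0.05, 0.10, 0.20 or 0.30. With SD 2.0 h it rises from 50% to between 54% and 65% over R² 0.10 to 0.30. With SD 1.0 h it is already 97%.

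**The case against.** **The t test is valid.** This stands. A reader might infer that the planned comparison is biased, or that chance imbalance in case mix is left uncorrected. The documents do not support that: allocation is random, and the t test's interval already allows for chance imbalance. Methods also states stratification by site and approach, although Allocation and Randomization names centre only.

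**The gain is assumed.** This also stands. No SD, R² or target difference for discharge time is given. There are reasons why R² could be low: operations of one to two hours, abdominal and pelvic surgery only, a standard anaesthetic protocol, and transfer to the DSU by two hours. At R² of 0.05 or below the gain is trivial. The 20-minute illustration also falls where adjustment shows to advantage. The only time effect in the documents is 25 minutes of PACU stay per PONV episode, which is a per-patient figure. If the whole 10-point planning difference were PONV, the arms would differ by 0.10 × 25 = 2.5 min, and power at SD 1.5 h would be about 6% unadjusted and 7% at R² 0.30. If 25 min were the between-arm difference, the t test would already have 90% power.

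**The outcome is not settled.** The objective allows discharge or readiness, and the documents do not say when the clock starts. End clock time plausibly affects actual departure, but much less clearly clinical readiness. It cannot be assumed that the same covariates help under either definition.

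**The timing of recording.** Appendix 1 takes these items from the surgical records, so they may be entered later. They are fixed before randomisation; nothing shows that they are recorded before it. Fixed is enough for a valid covariate.

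None of this supplies an adjusted model for hours, and the possible cost of adding one is about 0.5% in standard error.

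**Conclusion.** The point holds as a free improvement. Time to discharge has no adjusted analysis, although suitable covariates fixed before randomisation are already collected and at least one of them, site, is a stratification factor. The standard error would be multiplied by 0.975 to 0.837 for R² between 0.05 and 0.30, at a cost of about 0.5% if R² is zero. These figures assume 275 patients per arm with data and a linear model. Where R² falls in that range, or below it, cannot be learned from the documents.

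Two stronger readings should be resisted. One is that the plan contains an error or a biased comparison here; it does not. The other is that precision is certainly lost; that depends on how strongly the covariates predict discharge time, which the documents do not show. The primary outcome and its sample size are unaffected.

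**What to change.** Before unblinding, add to Statistical Analysis and to the Table 1 row for time to discharge:

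- A linear model of hours on treatment, site, laparoscopic/open and duration of surgery, reporting the adjusted mean difference with a robust 95% CI.
- If actual departure is the outcome, the clock time at which surgery ended as a further covariate, preferably in a flexible form.
- The unadjusted difference as a supporting result.
- A statement of when the clock starts and whether actual discharge or readiness is analysed.

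Reconcile the two descriptions of stratification at the same time. Approach belongs in the model either way, since it is fixed before allocation.

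The cost is a few sentences and one table cell, plus a decision on the outcome definition. No new data, visits or patients are needed. The covariates should be fixed before results are seen, because a later choice would be open to challenge.
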